Although there has been some evidence that encouraging oral fluid intake might decrease the morbidity of dengue infections, it is still uncertain whether oral fluid intake exerts a protective effect against the progression from non-severe to severe dengue . It is still unknown whether increasing oral fluid intake would alter the progression of dengue in terms of the degree of haemoconcentration and the fall in platelets.

Both of these parameters are routinely used for monitoring of both outpatients and hospitalized suspected dengue patients. Primary healthcare providers monitor these parameters very closely. Coupled with the clinical condition, primary physicians determine the necessity for hospital admission. Moreover, both these parameters constitute part of the warning signs mentioned in the WHO 2009 guidelines. However, it is still unknown whether increasing oral fluid intake in dengue patients will improve the mortality of dengue by lessening its progression or severity.

From the two studies looking at the effects of oral fluid intake, more questions arise. Should there be an association between oral fluid intake and the risk of hospitalization for dengue patients, an accurate estimation of the amount of fluid needed daily to achieve this effect is not known. The Nicaragua study collected data by retrospectively asking the patients how many glasses of fluid was ingested during the previous 24 hours. The findings are subject to recall bias. Moreover, there is a great variation in size of the glasses and cups used by the general population. Therefore an accurate estimate of the amount of fluid ingested daily could not be obtained.

The Taiwan study did not collect any data on the amount nor the type of oral fluids consumed by the patients in their oral hydration group. The only study that had some data on the types of fluids consumed by their patients was the study done in Nicaragua. Thus, little is known on the kinds of fluids that would be ideal for oral hydration in dengue patients. Such knowledge would greatly aid the primary healthcare members as well as other clinicians in providing accurate, evidence based advice regarding the quantity and types of fluids for dengue patients to consume in order to avoid hospitalization.

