# Study objectives

- 1. To determine the feasibility of the designed research process in terms of the following:
  - a. Recruitment/retention of participants
  - b. Randomisation of the participants.
  - c. Logistics manpower, resources
- 2. To determine the feasibility and acceptability of the designed intervention in terms of the following:
  - a. Usage of the cups as a standardized measure of fluid intake
  - b. Usage of the fluid charts as a tool for behaviour change
  - c. The implementation process of the intervention
- 3. To determine the trend of the preliminary results in order to:
  - a. To estimate the treatment effect size of the experimental intervention
  - b. To calculate the sample size for the main evaluation randomized controlled trial.
- 4. To refine the research process and intervention design for the main evaluation randomized controlled trial.

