#### Method of intervention received by the control group only

Apart from this, the control group will be asked their twenty four hour fluid recall. This means that the patient will be asked to give an estimate of how much fluid they have drunk in the twenty four hours prior to the current consultation with the researcher or the trained research assistants.

This estimate will be given by the patients in terms of how many litres or millilitres of fluid they drank, how many glasses (small or large sized glasses or mugs), or how many bottles of drinks they had (500ml size, 1 litre size, or 1.5 litre size), or how many packet drinks they had. Details on what type of fluids is consumed orally will be obtained. This information will be obtained during recruitment of the patient, and on each subsequent follow-up.

One should take note that no fluid chart or cup will be given to the control group participants.

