## Method of intervention received by the intervention group

The patients assigned to the intervention group will be given a plastic cup of uniform size, along with a twenty four hour fluid chart. These patients will be instructed to use the cup for drinking any form of fluid they wish to consume for the duration of their participation in the study. Verbal instructions will be given on how to fill in the various details required on the fluid chart regarding their oral fluid consumption.

This will be done over the next twenty four hours or until they come for their next follow-up consultation at the clinic. If the next clinic follow-up will be given at the interval of a few days after the preceding consultation, then the researcher or the trained research assistant will provide enough fluid chart forms for the patient to fill until the next consultation.

The patient will be instructed to write down the amount of fluids they drank according to the time that they consumed the fluids in the second column. The patients will be instructed to record the type of fluids they drink in the third column. The patient will only fill the last column if they received any intravenous fluid drip over the next twenty four hours. They are to record the amount of bottles of fluid they receive intravenously.

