## Amount of fluid in the cups used for the intervention group

Each of the uniform sized cups used in the intervention group contains up to 175 ml of fluids. The principal researcher measures the amount of fluid a cup will contain by filling the cup with water using a syringe to estimate the amount.

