## Conversions used for calculation of total fluid intake

The author has to make several assumptions to ease the calculation of total oral fluid intake, due to the very nature of the data collected from the patients. It is found that patients used a variety of containers of varying shapes and sizes for their daily oral fluid intake.

- For the control group, each glass that the patient reported at home contained 175 ml of fluids, which is equivalent to the amount of fluid contained in the cup used in the intervention group.
- A regular, standard sized mug contains 250 ml of fluids (the principal researcher measured the amount of fluid a mug of such size will contain by filling the mug with water using a syringe to estimate the amount).
- One large cup used by the patient at home is equivalent to one mug, which contains 250ml of water.
- One plastic bag of drinks bought from the hawker stall is equivalent to three cups of water
- One small packet drink contains 250 ml of fluid (as is written on the packet drink itself).
- One can drink contains 325 ml of fluid (as is written on the can itself).
- One small bottle of mineral water contains 500 ml of fluid (as is stated on the bottle label itself).
- One big bottle of drinks contain 1000 ml of fluid (as is stated on the bottle label itself).
- One large bottle of drinks contain 1500 ml of fluid (as is stated on the bottle label itself).
- One jug of water contains 1000 ml of fluid

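### Every control-group glass is converted at 175 ml, the study cup's capacity rather than a measured home glass, so the between-arm intake difference carries a bias of unknown direction

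*Protocol*

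**What the plan says.** Control patients estimate their last 24 hours of intake by recall. Under the method for the control group they may answer in litres or millilitres, bottles, packets, or "how many glasses (small or large sized glasses or mugs". They receive neither chart nor cup.

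The section on conversions then fixes the volumes. For glasses the rule is: "For the control group, each glass that the patient reported at home contained 175 ml of fluids", and the reason given is "which is equivalent to the amount of fluid contained in the cup used in the intervention group". A mug is 250 ml, measured by syringe. A large cup used at home is set equal to a mug. Packets, cans and bottles are taken from their labels. A small glass or a large glass has no entry.

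Intervention patients are told to drink everything from the study cup. On its volume the Protocol says: "Each of the uniform sized cups used in the intervention group contains up to 175 ml of fluids", obtained because the researcher "measures the amount of fluid a cup will contain by filling the cup with water using a syringe". For the chart, "The patient will be instructed to write down the amount of fluids they drank according to the time that they consumed the fluids". No unit and no rule for a part-filled cup is given there.

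The Background criticises the Nicaraguan study's glass counts because "there is a great variation in size of the glasses and cups used by the general population". The Preliminary outcome measures section lists the between-group difference in oral fluid intake as item 5.

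**The concern.** The 175 ml home glass is a convenience value. It makes the two arms look as if they share one unit, but only the intervention arm uses the vessel from which the number came. If home glasses average something else, every control intake reported in glasses is scaled by the same wrong factor and intervention intake is not. That is bias in the contrast, not noise, and recruiting more patients does not reduce it.

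The Protocol faults an earlier study on just this ground, and the study objectives include "Usage of the cups as a standardized measure of fluid intake". Assigning the cup's volume to vessels nobody has measured gives up that advantage in the control arm.

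The study exists to judge whether a chart can raise oral intake and to estimate the size of that effect. A spurious difference, or a true one masked, would mislead both judgements.

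**Working it through.** There is no stated figure to reproduce: the 175 ml glass is an assumption, and the minimum of 30 per group has no derivation. The check is therefore a bias calculation.

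**Inputs from the Protocol.** Control glass counted at 175 ml; study cup capacity 175 ml; mug or large cup 250 ml; at least 30 patients per group; Student's t test; p<0.05 (taken as two-sided).

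**Assumptions, not in the Protocol.** True intake T = 2,000 ml/day in both arms; a home glass delivers g = 150 to 200 ml; SD 500, 700 or 1,000 ml; all or half of control intake reported in glasses, the rest converted correctly; study cups counted correctly.

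**Step 1: scaling error in the control arm.** Counted/true = 175/g.
- g = 200: 175/200 = 0.875, an understatement of 12.5%.
- g = 175: no error.
- g = 150: 175/150 = 1.167, an overstatement of about 17%.

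**Step 2: spurious difference (intervention minus control).** Difference = T × share in glasses × (1 − 175/g).
- g = 200, all in glasses: 2,000 × 0.125 = +250 ml/day.
- g = 200, half in glasses: 2,000 × 0.5 × 0.125 = +125 ml/day.
- g = 150, all in glasses: 2,000 × (1 − 1.1667) = −333 ml/day, so the chart appears harmful.

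**Step 3: chance of p<0.05 with no true difference.** Noncentral t with 58 degrees of freedom, critical value 2.002, noncentrality = difference / (SD × √(2/30)).

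| Spurious difference | SD 500 | SD 700 | SD 1,000 |
|---|---|---|---|
| 250 ml (all in glasses) | 48% | 28% | 16% |
| 125 ml (half in glasses) | 16% | 10% | 8% |

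The nominal rate is 5%. With 100 per arm and SD 700, the 250 ml artefact reaches significance in about 71% of trials: a larger sample makes the bias easier to detect as an effect but does not shrink it.

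**Step 4: the study cup (secondary).** 175 ml is the cup when filled. A cup filled to 90% holds 157.5 ml; if logged as one cup it counts as 175 ml, an excess of 175/157.5 = 1.111, or 11%. Whether this happens depends on how patients and staff write the amount, which the Protocol does not settle.

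**The case against.** Four points on the other side carry weight.

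- **The rule touches only part of control intake.** Answers in millilitres, bottles, cans and packets are converted directly or from labels, and mugs and large cups get 250 ml. A large glass might be coded as a large cup. This stands as a limit on size, and is why the half-in-glasses row is shown. It does not remove the gap, because nothing tells staff to code a large glass that way.
- **A reader might infer a worst case from 250 ml glasses:** a 30% understatement, 600 ml/day, and about a 90% false-positive rate at SD 700. The Protocol does not support this as a typical case. It would need all control intake to come from 250 ml vessels with none coded as a mug or large cup, yet those are the vessels already credited with 250 ml.
- **A reader might infer that every study cup is counted as full,** and that identical intake would then look 27% higher in the intervention arm (200/175/0.9). No section states that rule; patients write an amount, and staff clarify the entries at follow-up. The 27% also assumes part-filled study cups but full home glasses. With 90% fill in both arms a 200 ml glass delivers 180 ml, and the excess is 1.111/(175/180) = 1.14, or 14%.
- **A reader might infer that the bias favours the chart and goes straight into the main-trial sample size.** Glasses below 175 ml reverse it. The Protocol names no primary outcome and does not say that intake will drive the sample size; intake is one of five preliminary outcomes.

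It is also fair that the conversions are openly labelled as assumptions and that refining the process is a pilot objective. Nor can it be said that glass size is recorded and then discarded, since the data collection form is not shown. None of this justifies an unmeasured constant acting on one arm of a comparison.

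**Conclusion.** The concern holds in a limited form. As written, the conversion rule puts an arm-specific error of unknown sign into the intake difference: 12.5% too low for control intake reported in glasses if glasses deliver 200 ml, about 17% too high if they deliver 150 ml. Under the assumptions above, with 200 ml glasses, the false-positive rate at 30 per arm is about 16% to 48% if all control intake is in glasses and about 8% to 16% if half is.

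These sizes rest on assumed glass volumes, intake, SD and reporting mix, for which the Protocol gives no figures. What rests on the text alone is that 175 ml is not a home-glass measurement, that a small or large glass has no volume, and that only the control arm is exposed. Overcounting of part-filled study cups is a possibility left open, not a stated rule. The change should be made before intake results are interpreted.

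**What to change.** - Replace the single 175 ml rule. At each recall, record glass size as small, standard or large against a neutral graduated container or a picture, and convert by the recorded size, with a stated volume for each category, including a large glass. Do not use the study cup as the reference: it is part of the intervention, and showing it to controls at every visit would expose them to it.
- In the intervention arm, have patients record part cups, and have staff confirm them when they clarify chart entries at follow-up.
- Report the intake difference with the control glass set at 150, 175, 200 and 250 ml. If the conclusion changes across that range, say so.
- State as a limitation that retrospective recall and a prospective chart are different measurements. Better conversion does not remove that difference between arms.

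Cost: Protocol wording, one field on the recall form, a reference container or picture, and a slightly longer interview. No additional patients or visits are needed.
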